Part A of the study is a non-randomised 6 period, sequential, 6-way fixed sequence design in which up to 4 MR minitab formulations in a capsule may be evaluated following single dose administration in the fasted state (120 mg). Periods 1, 2 and 3 will evaluate a slow MR release duration (nominally 24 hours), a fast MR release duration (nominally 10 hours), and IR tablet, respectively. Periods 4, 5 and 6 will be flexible and the dosing regimen will be dependent on the outcome of Periods 1 to 3. In Periods 4 to 6,

there will be the option to optimise the MR release duration and/or to evaluate the impact of food (high-fat meal) on the selected MR minitab formulation in a capsule. There will also be the option to cancel Periods 5 and 6 if an optimal formulation is determined in Periods 1 or 2.

Part B of the study will be an open-label, repeat dose study in which the selected MR minitab formulation in a capsule will be evaluated following 3 days repeat dosing of GSK2982772 at target daily doses of 30, 60 and 240 mg. In Part B, administration of the MR minitab formulation in a capsule will either be in the fasted state or with a standard meal (non-high fat), depending on the results of the food effect assessment in Part A. The prandial state for each dosing period may be selected as fasted or fed (standard meal) but within each dosing period, all doses will be administered in the same prandial state. The frequency of dosing in Part B will either be QD or BID depending on the PK profile in Part A. Whether dosing is QD or BID, the total daily doses will remain the same.

Part C of the study is a non-randomised 6 period, sequential, fixed sequence crossover design in which MR tablet formulations will be evaluated. Periods 1 and 2 will evaluate single dose administration of a 240 mg MR tablet and the 240 mg IR tablet (reference), respectively. Periods 3, 4, 5 and 6 will be flexible and the dosing regimen will be dependent on the outcome of Periods 1 and 2. In Periods 3 to 6, there will be the option to evaluate higher doses, the impact of a high-fat meal and/or standard meal after dosing or BID dosing.

Number of Participants:

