Sixteen participants will be enrolled into Part A of the study to allow for the completion of at least 12 evaluable participants. An evaluable participant will have completed the planned safety and PK assessments up to 32 hours after dosing (or 24 hours after dosing for Period 3; IR regimen). An evaluable participant must also have received the relevant test and reference formulations for the comparisons of interest e.g. an MR formulation and the IR reference and/or the selected MR formulation in both the fed and fasted states.

Ten participants will be enrolled into Part B of the study to allow for the completion of at least 6 evaluable participants. An evaluable participant will have received all 3 doses and completed the planned safety and PK assessments up to 24 hours after the last dose.

In Part C, 16 participants will be enrolled such that at least 12 evaluable participants complete the study. An evaluable participant will have completed the planned safety and PK assessments up to 32 hours after dosing (or 24 hours after dosing for Period 2; IR regimen). An evaluable participant must also have received the relevant test and reference formulations for the comparisons of interest e.g. the MR tablet and the IR reference at 240 mg.

Treatment Groups and Duration:

In Part A, each participant will be enrolled in the study for approximately 8 to 13 weeks, dependent on screening and washout duration between periods. Participation will include a screening evaluation within 28 days of study treatment administration and up to 6 separate inpatient periods. Participants will be admitted to the clinic in the morning of the day before dosing (i.e. Day -1) of each inpatient period. Each inpatient period will consist of 3 days and 2 nights followed by a minimum washout of 7 days between doses.

A follow-up visit will occur at least 7 days after the last study treatment. Participants will receive a single oral dose of study treatment during each inpatient period.

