Descriptive statistics (n, arithmetic mean, standard deviation [SD], 95% CI, minimum, median and maximum,) will be calculated by treatment for all PK concentrations over time and for the derived PK parameters. In addition, for loge-transformed PK parameter variables geometric mean, 95% CI and $\%CV_b$ ($100 * \sqrt{(\exp(SD^2) - 1)}$) will be provided, where the SD is the standard deviation of log-transformed data.

Endpoint	Statistical Analysis Methods
Primary	
The primary PK endpoints to compare MR formulations with IR formulations will be summarised descriptively. Ratio of $AUC_{(0-inf)}$, $AUC_{(0-24)}$, ($AUC_{(0-t)}$, if $AUC_{(0-inf)}$ cannot be derived), C_{max}, C_{12} and C_{24} for MR formulation to IR formulation will be computed with 90% CI. C_{max} to C_{12h} and C_{max} to C_{24h} ratio for each MR formulation (120 mg or 240 mg) and the corresponding total dose of IR formulation (120 mg or 240 mg) will be computed with 90% CI.

Secondary	
The secondary endpoints for food effect will be summarised descriptively. In addition, log-transformed $AUC_{(0-inf)}$ ($AUC_{(0-t)}$, if $AUC_{(0-inf)}$ cannot be derived), C_{12h}, C_{24h}, and C_{max} will be analysed using a mixed effects model with regimen as a fixed effect and subject within sequence as a random effect. Point estimates and corresponding 90% CI will be computed for the differences for each GSK2982772 MR formulation (120 mg, 240 mg, 360 mg or 480 mg) taken in the fed state (test) vs the same dose in the fasted state (reference) using the residual error from the model (MSE). The point and interval estimates on the log-scale will then be exponentially back transformed to give estimates of the ratios of geometric means and 90% CI.
 
Within-subject coefficients of variation for $AUC_{(0-inf)}$ and C_{max} will be calculated based on the log_e-Normal distribution: $CV_w (\%) = \sqrt{\exp(mse) - 1} \times 100$, where MSE is the residual error from the model.
 
Statistical analysis of the PK endpoint T_{max} of each GSK2982772 MR formulation administered under both fed and fasted conditions will be separately analysed non-parametrically [Hauschke, 1990]. The point estimates for the medians for each treatment, the median difference and 90% CI for the median difference will be calculated for the contrast (test-reference).

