### 8.2.5.1. Statistical Methodology Specification (Part A)

Endpoint (log scale)

 
• <math>AUC_{(0-\infty)}</math>
 
• <math>AUC_{(0-t)}</math> if <math>AUC_{(0-\infty)}</math> cannot be derived
 
• <math>C_{max}</math>
 

Model Specification

 
• For each endpoint a mixed model will be fit with 2 observations per subject expected. The model will contain state [[fed/faasted] as a fixed, categorical effect and a random intercept for subject.
 
• The Kenward & Roger (KR) degress of freedom approach will be used.
 

Model Checking & Diagnostics

 
• See Section 8.1.5.1
 

Model Results Presentation

 
• Point estimates and corresponding 90% CI will be computed for the differences in the endpoint for GSK2982772 MR formulation (120 mg) taken in the fed state (test) vs in the fasted state (reference) using the residual error from the model (MSE).
 
• The point and interval estimates on the log-scale will then be exponentially back transformed to give estimates of the ratios of geometric means, <math>F_{rel,FE}</math>, and 90% CI. See Section 10.6.4
 

Endpoint

 
• <math>T_{max}</math>
 

Model Specification

 
• Exact non-parametric Hodges-Lehmann estimation of location shift will be fitted.
 
• Only the dose of GSK2982772 administered under both fed and fasted conditions will be used.
 

Model Results Presentation

 
• GSK2982772 MR formulation in fed (test) will be compared to fasted (reference) state.
 
• Median difference and 90% CI for median difference will be presented.
 

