## Bioavailability of Dose

Endpoint (log scale)

 
• <math>AUC(0-\infty)</math>
 
• <math>AUC(0-t)</math> if <math>AUC(0-\infty)</math> not available
 
• <math>AUC(0-24)</math>
 
• <math>C_{max}</math>
 
• <math>C_{24}</math>
 

Model Specification

 
• For each endpoint a mixed model will be fit with 2 observations per subject expected. The model will contain dose (480 mg and 240 mg in the fasted state) as a fixed, categorical effect, and a random intercept for subject.
 
• The Kenward and Roger method for approximating the denominator degrees of freedom and correcting for bias in the estimated variance-covariance of the fixed effects will be used.
 

Model Checking & Diagnostics

See Section 8.1.5.1.

Model Results Presentation

Point estimates and corresponding 90% CI will be computed for the differences in the endpoint for GSK2982772 MR dose (480 mg vs 240 mg) using the residual error from the model (MSE).

The point and interval estimates on the log-scale will then be exponentially back transformed to give estimates of the ratios of geometric means, <math>F_{relDOSE}</math>, and 90% CI. See Section 10.6.4

Endpoint

Tmax

Model Specification

Exact non-parametric Hodges-Lehmann estimation of location shift will be fitted.

Only GSK2982772 administered at 240 mg and 480 mg.

Model Results Presentation

GSK2982772 MR formulation at 480 mg (test) state will be compared to 240 mg (reference).

Median difference and 90% CI for median difference will be presented.

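### The SAP's Tmax blocks do not tie the Hodges-Lehmann estimate and 90% CI to within-subject differences; read literally they describe the independent-samples form

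*SAP*

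**What the plan says.** **Tmax.** SAP 8.2.5.1 (Part A, fed against fasted) states: "Exact non-parametric Hodges-Lehmann estimation of location shift will be fitted". The data rule is "Only the dose of GSK2982772 administered under both fed and fasted conditions will be used", and the output rule is "Median difference and 90% CI for median difference will be presented". The Part C food-effect block in 8.2.5.3 repeats all of this. The Part C dose block (480 mg against 240 mg) uses the same estimator, and its data rule is "Only GSK2982772 administered at 240 mg and 480 mg". No Tmax block mentions subject, pairing, within-subject differences or signed-rank limits.

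**AUC and Cmax in the same sections.** In Part A, "For each endpoint a mixed model will be fit with 2 observations per subject expected", with a random intercept for subject. The Part C dose model is built the same way and is limited to the fasted state.

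**Protocol.** Section 10.4.1 calls for a non-parametric analysis in which "the median difference and 90% CI for the median difference will be calculated for the contrast (test-reference", and cites a distribution-free procedure for bioequivalence studies. SAP section 9 lists that reference, but the Tmax blocks do not cite it.

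**Design.** Part A is a "non-randomised 6 period, sequential, 6-way fixed sequence design", and Part C is also a six-period fixed sequence. On numbers: "Sixteen participants will be enrolled into Part A of the study to allow for the completion of at least 12 evaluable participants"; Part C has the same targets.

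**Who is analysed.** The PK population (SAP section 4) is any dosed participant with an analysed PK sample. SAP 8.1.4 keeps all available data from withdrawn participants, and replacements generally start at the withdrawn participant's next treatment.

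**Formulation tables.** SAP Tables 3.5 and 3.18 promise a statistical analysis of Tmax by formulation, but Tmax is not among the endpoints of 8.1.5.1 and no method is given for it.

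**The concern.** An exact Hodges-Lehmann estimate exists in two forms. One takes the median of all between-group differences, with Mann-Whitney limits. The other takes the median of the Walsh averages of within-subject differences, with signed-rank limits. Location shift normally names the first. A programmer following the Tmax text as written could therefore run the independent-samples procedure on data in which the same people supply both columns.

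That interval takes no account of within-subject correlation. If Tmax is positively correlated between periods, the interval is wider than it need be, and a real delay or advance with food could look compatible with no change. If the correlation is negative, the interval is too narrow.

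Tmax is a named secondary endpoint for food effect in Parts A and C and for dose in Part C, and this 90% CI is the only inferential output planned for it.

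The dose block has a further gap. Under SAP 5.1, Part C gave the 240 mg MR tablet in two prandial states and 480 mg in three. Without the fasted restriction, a participant could contribute five MR values, and food would be mixed with dose.

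**Working it through.** The plan states no precision, power or sample size for Tmax, so there is no Tmax figure to reproduce.

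**1. What the text leaves open.** The Tmax data rules restrict doses, not participants. The evaluable-participant definition (protocol 5.2) requires both test and reference, but it governs enrolment targets and interim decisions, not the analysis set. Nothing in the SAP's population or replacement rules forces pairing.

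**2. Large-sample guide.** With common variance σ² in both periods and within-subject correlation ρ:
- unpaired width is proportional to √(2σ²/n)
- paired width is proportional to √(2σ²(1−ρ)/n)
- the ratio is therefore about 1/√(1−ρ)

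**3. What ρ might be.** The documents give no value for Tmax. The only proxy is the AUC and Cmax variability in protocol 10.2.3, using s² = ln(1+CV²):

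- AUC: ln(1+0.309²)/ln(1+0.487²) = 0.0912/0.2128 = 0.43
- Cmax: ln(1+0.367²)/ln(1+0.585²) = 0.1264/0.2943 = 0.43

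Protocol 10.4.1 and SAP 8.1.2 compute CVb by treatment from the SD of the log values. That SD contains the within-subject part, so ρ = 1 − 0.43 = 0.57. Only if CVb were purely between-subject would ρ be 1/(1+0.43) = 0.70. At 0.57 the guide in step 2 gives 1/√0.43 = 1.52.

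**4. Exact intervals by simulation.** Settings: n = 12, 4,000 runs per case, bivariate normal, assumed SD 4 h and shift 2 h. The SD cancels from the continuous-case ratio. Unpaired limits are the 43rd smallest and 43rd largest of the 12 × 12 = 144 between-group differences. Paired limits are the 18th smallest and 18th largest of the 12 × 13/2 = 78 Walsh averages.

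| ρ | Unpaired width (h) | Paired width (h) | Ratio | Unpaired coverage | Paired coverage | Ratio, 2-h grid |
|---|---|---|---|---|---|---|
| -0.3 | 5.91 | 6.86 | 0.86 | 87.4% | 91.4% | 0.86 |
| 0 | 5.90 | 6.00 | 0.98 | 91.2% | 90.6% | 0.97 |
| 0.3 | 5.90 | 4.99 | 1.18 | 95.4% | 90.7% | 1.17 |
| 0.5 | 5.89 | 4.27 | 1.38 | 97.6% | 90.6% | 1.37 |
| 0.57 | 5.84 | 3.96 | 1.47 | 98.3% | 90.3% | 1.46 |
| 0.7 | 5.78 | 3.30 | 1.75 | 99.2% | 91.2% | 1.71 |
| 0.9 | 5.58 | 1.90 | 2.94 | 100% | 91.1% | 2.69 |

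Coverage is for continuous Tmax. Ratios at n = 16 are within 0.04 of these.

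**5. Effect of the sampling grid.** With Tmax rounded to the 2-h MR sampling times, the width ratios barely change but neither interval is exact. At n = 12 the paired interval covers 95% to 99% and the unpaired one 96% to 100%, so the shortfall at ρ = -0.3 disappears. Pairing alone does not restore exactness when there are ties.

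**The case against.** The SAP never says two-sample or unpaired, and a Hodges-Lehmann estimate from paired differences is equally standard. The protocol's test-minus-reference median difference fits a paired analysis. The protocol also cites a specific procedure, which may settle the matter and cannot be consulted here. SAP 2.1 declares no departure from the planned analysis under the original protocol and amendment 1. This stands as far as it goes: the defect is an incomplete specification whose literal reading is the wrong one, not an explicit choice of the wrong analysis.

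A reader might go further and infer that the Tmax interval is certain to be far too wide, perhaps by a factor of about 1.75 with 99% coverage. The documents do not support that. The factor needs a correlation of 0.70, which contradicts their own definition of CVb. Even 0.57 comes from AUC and Cmax, not Tmax. At zero correlation the two widths are nearly equal, and below zero the unpaired interval is the narrower one.

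The paired form also has a cost. Because of withdrawals and replacements, some participants may have only one of the two periods, and they would be lost from this analysis.

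Finally, no formal hypothesis is tested, no decision rule uses the Tmax interval, and individual Tmax values are listed and profiles plotted by subject, so within-subject shifts remain visible. That limits the consequence but does not remove the ambiguity.

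**Conclusion.** The concern holds as an under-specification. The contrasts are within-subject, the AUC and Cmax models beside them respect that, and the Tmax wording does not.

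If the unpaired form were run, the interval would be a true 90% CI only near zero correlation. At the 0.57 proxy it would be about 1.5 times the paired width, with coverage of about 98%. Across the assumed range of ρ, the ratio runs from 0.86 to 2.9. For continuous Tmax, the paired interval stays at 90% to 91% throughout.

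These figures assume 12 participants, bivariate normal Tmax with equal variances, and a correlation that the documents do not supply. The effect is confined to the precision and calibration of a secondary, descriptive interval. The correction is cheap enough to be worth making.

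**What to change.** - **Three Tmax blocks (8.2.5.1 and both in 8.2.5.3).** State that the estimate is the median of the Walsh averages of within-subject test-minus-reference differences, with a 90% CI from signed-rank limits, in participants with both values. In the Part C food-effect block, form each difference between fed and fasted at the same dose, as protocol 10.4.1 already requires.
- **Ties and zeros.** State how they are handled. The MR sampling times are 2 h apart, so differences will cluster at multiples of 2 h, including zero. SAP 8.2.1.2 bases parameters on actual sampling times, which may break some ties by minutes; the rule should say whether such near-ties count as ties.
- **Part C dose block.** Restrict Tmax to the fasted 240 mg and 480 mg MR regimens, as the AUC and Cmax dose model does.
- **Tables 3.5 and 3.18.** Add the same paired method to 8.1.5.1, which has none for Tmax.

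The cost is a few sentences and a different procedure call, plus the loss of participants with a single period. The number contributing pairs should be shown in each table.

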### 8.2.5.2. Statistical Methodology Specification (Part B)

Endpoint (log scale)

 
• <math>AUC_{(0-24h)}</math> (QD)
 
• <math>AUC_{(0-12h)}</math> (if BID)
 
• <math>AUC_{(12-24h)}</math> (if BID)
 
• <math>C_{max}</math> (morning) (QD or BID)
 
• <math>C_{max}</math> (evening) (if BID)
 

Model Specification

 
For each endpoint a mixed model will be fit with 6 observations per subject expected. The model will contain dose (120, 240, 300) and day (1,3) as fixed, categorical effects, and their interaction.
 
A direct product (UN@CS) covariance pattern will be fit using period and day (in that order) as the effects in the REPEATED statement.
 
The Kenward & Roger (KR) degrees of freedom approach will be used.
 

Model Checking & Diagnostics

 
See Section 8.1.5.1. Additionally, in the event the model fails to converge a compound symmetric covariance pattern will be fit using day*dose as the effect on the REPEATED statement, with type=CS, group=period, and subject id specified in the subject= option to account for the correlation between days within period. A random intercept effect will also be included to account for the correlation between days across period.
 
In the event the above model fails to converge, a compound symmetric covariance pattern will be fit using day*dose as the effect on the REPEATED statement, with type=CS and subject id specified in the subject= option. A random period effect will also be included.
 
In the event the above model fails to converge, a compound symmetric covariance pattern will be fit using day*dose as the effect on the REPEATED statement, with type=CS and subject id specified in the subject= option.
 
In the event the above model fails to converge, all other covariance patterns will be explored, including unstructured.
 
If outliers are detected, an additional table will be produced with outlying observations omitted.
 

Model Results Presentation

 
Point estimates and corresponding 90% CI will be computed for the differences in the endpoint between Day 1 and Day 3 for Period 1 (120mg daily), Period 2 (240mg daily), and Period 3 (300mg daily) for GSK2982772 minitab MR dose.
 
The point and interval estimates on the log-scale will then be exponentially back transformed to give estimates of the ratios of geometric means, <math>F_{relDay}</math>, and 90% CI. See Section 10.6.4
 

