### 2.2. Study Objective(s) and Endpoint(s)

[figure not shown]
Objectives	Endpoints
Primary Objectives	Primary Endpoints

 
To evaluate the single dose PK profile of GSK2982772 from each test minitab Modified Release (MR) formulation in a capsule (120 mg) compared to the IR formulation (120 mg)
 
	
 
GSK2982772 area under the curve from time zero to infinity (AUC(0-inf)), area under the curve from time zero to the last measurable concentration AUC(0-t), area under the curve from time zero to 24 hours AUC(0-24), area under the curve from time zero to 12 hours AUC(0-12), maximum observed concentration (Cmax), Concentration at 12 hours post-dose (C12h), Concentration at 24 hours post-dose (C24h) and ratio of Cmax : C12h and Cmax : C24h, relative bioavailability (Frelformulation) based on AUC and Cmax
 

 
To evaluate the single dose PK profile of GSK2982772 from a (matrix monolithic) MR tablet (240mg) compared to the IR formulation (240mg).
 
	
 
GSK2982772 AUC(0-inf), AUC(0-t), AUC(0-24), AUC(0-12), Cmax, C12h, C24h, Cmax:C12h and Cmax:C24h, Frelformulation based on AUC and Cmax.
 

Secondary Objectives	Secondary Endpoints

 
To assess the impact of high fat meal on the PK of GSK2982772 following single dose
 
	
 
GSK2982772 AUC(0-inf), AUC(0-t), Cmax, time to Cmax (Tmax), FrelFE based on AUC and Cmax,
 

Objectives	Endpoints
administration of the selected minitab MR formulation in a capsule (120 mg)	

 
To determine if there are any dose dependant changes in the absorption of GSK2982772 following repeat dose administration of the selected minitab MR formulation in a capsule at target daily doses of 30, 60 and 240 mg
 
	
 
GSK2982772 AUC(0-24), Cmax, and Tmax if once daily (QD) dosing, on Day 1 and Day 3
 
GSK2982772 AUC(0-12), AUC(12-24), Cmax, and Tmax after morning dose, Cmax and Tmax after evening dose if twice daily (BID) dosing, on Day 1 and Day 3
 

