### 8.2.2. Summary Measure

For each fed/faasted state in Parts A and C, and for day 1 and day 3 of every dose (period) in Part B, descriptive statistics (n, arithmetic mean, standard deviation [SD], 95% CI, minimum, median and maximum,) will be calculated by treatment for all PK concentrations over time and for the derived PK parameters. In addition, for loge-transformed PK parameter variables geometric mean, 95% CI and % $CV_b$  will be provided, where % $CV_b$  =  $(100 * \sqrt{(\exp(SD^2) - 1)})$  and SD is the standard deviation of log-transformed data.

For Part B, log-scale dose normalized  $C_{\max}$ ,  $C_{12h}$  (for BID),  $C_{24h}$ ,  $AUC_{(0-12)}$  (for BID dosing)  $AUC_{(12-24)}$  (for BID dosing), and  $AUC_{(0-24)}$  will also be summarized. Plots of dose vs log-scale dose normalised  $AUC_{(0-24)}$ , ( $AUC_{(0-12)}$  and  $AUC_{(12-24)}$  for BID dosing),  $C_{12h}$  (for BID),  $C_{24h}$ , and  $C_{\max}$  (after morning and evening doses if BID dosing) will be generated to determine if there are any dose dependent changes in the absorption of GSK2982772 following repeat dose administration of the selected minitab MR formulation.

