
Relative Bioavailability (F rel )	

 
Frel will be calculated as follows:
 
	
$F_{rel} = \frac{GeoMean\{AUC \text{ or } C_{max}(\text{test})\}}{GeoMean\{AUC \text{ or } C_{max}(\text{reference})\}} \times 100$	
F rel will be calculated using AUC (0-∞) and C max . If for any reason the AUC (0-∞) is not calculable then an alternative AUC such as AUC (0-last) , AUC (0-T) or AUC over a partial area may be used. The following comparisons will be made: 
 
MR Formulation (test) vs IR Formulation (reference)
 
Fed (test) vs Fasted (reference)
 
Day 3 vs Day 1 (reference)
 
	

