## 10.11.7.2. Pharmacokinetic Tables Part B

Pharmacokinetic: Tables					
No.	Population	IDSL / TST ID / Example Shell	Title	Programming Notes	Deliverable [Priority]
PK Concentration					
3.8.	PK	PK01	Summary of Plasma GSK2982772 Pharmacokinetic Concentration-Time Data by Dose and Day: Part B		SAC
PK Derived Parameters					
3.9.	PK	PKPT1	Summary Statistics of Derived Plasma GSK2982772 Pharmacokinetic Parameters by Dose and Day: Part B	Parameters with units	SAC
3.10.	PK	PKPT3	Summary Statistics of Log-Transformed Derived Plasma GSK2982772 Pharmacokinetic Parameters by Dose and Day: Part B	Parameters with units	SAC
3.11.	PK	PKPT3	Summary Statistics of Log-Transformed Derived Plasma GSK2982772 Dose-Normalized Pharmacokinetic Parameters by Dose and Day: Part B	Parameters with units	SAC
PK Analyses					
3.12.	PK	PK_T2	Summary of Statistical Analysis of Plasma GSK2982772 PK Parameters (AUC & C) Assessing Relative Bioavailability of Repeat Dose: Part B		SAC

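### Part B's dose-dependence objective gets per-dose means and plots but no between-dose ratio with a CI, although the planned mixed model can supply one for 240 mg vs 120 mg

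*SAP*

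**What the plan says.** SAP 2.2 gives the Part B secondary objective as "To determine if there are any dose dependant changes in the absorption of GSK2982772 following repeat dose administration of the selected minitab MR formulation". The target daily doses were 30, 60 and 240 mg. SAP 2.3 gives the actual daily doses as 120, 240 and 300 mg, and SAP 5.1 labels the first two fasted and the third fed with a standard meal.

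Two strands of analysis follow.

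- **Descriptive.** SAP 8.2.2 summarises dose-normalised parameters on the log scale, with geometric means and 95% CIs. It adds plots against dose, which "will be generated to determine if there are any dose dependent changes in the absorption of GSK2982772 following repeat dose administration". Table 3.11 (by dose and day) and Figure 3.12 (individual values with geometric mean and 95% CI against dose) carry this.
- **Modelled.** SAP 8.2.5.2 fits a mixed model to log AUC and log Cmax: "The model will contain dose (120, 240, 300) and day (1,3) as fixed, categorical effects, and their interaction". Under its results presentation, "Point estimates and corresponding 90% CI will be computed for the differences in the endpoint between Day 1 and Day 3", separately for each period. The output, Table 3.12, is titled as "Assessing Relative Bioavailability of Repeat Dose: Part B". The comparisons listed for relative bioavailability in SAP 10.6.4 are MR against IR, fed against fasted, and Day 3 against Day 1. None is between doses.

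For Part C, SAP 8.2.5.3 specifies a modelled 480 mg vs 240 mg ratio with a 90% CI (FrelDOSE).

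**The concern.** The one modelled output in Part B compares days within a dose, whereas the objective asks about differences between doses. The dose term is fitted but never reported as a contrast. A reader of the study report would have to judge dose dependence by setting separate per-dose intervals side by side. That discards the within-subject pairing, and it yields no statement of how large a change in dose-normalised exposure the data allow. Part C, with the same kind of objective, gets such a statement, and the documents give no reason for the difference. The stake is modest: how firmly Part B can speak to dose proportionality of the minitab formulation.

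**Working it through.** **Inputs.** Protocol 10.2.2 (Part B) gives CVw of 17.6% for AUC and 23.2% for Cmax, CVb of 27.1% and 36.1%, and 8 completers. The text lists the two CVb values and the two CVw values in opposite parameter order, so I use ranges. Protocol 5.2 gives 10 enrolled and at least 6 evaluable. Protocol 10.2.3, using Part A of this study, gives CVw of 30.9% and 36.7% and CVb of 48.7% and 58.5%. Throughout, σ = √ln(1 + CV²).

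**1. Reproduce the plan's figure.** For a single mean, the upper half-width of the 90% CI is exp(t(0.95, n−1)·σ/√n) − 1. With n = 8, t = 1.8946:
- CVw 17.6%: σ = 0.1747, exp(0.1170) − 1 = 12.4% (protocol 12.1%)
- CVw 23.2%: σ = 0.2290, exp(0.1534) − 1 = 16.6% (protocol 16.7%)

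All 16 cells of protocol Table 6 reproduce within 0.4 points.

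**2. What the planned displays give.** For a per-dose geometric mean, the upper half-width of the 95% CI is exp(t(0.975, n−1)·σb/√n) − 1. With n = 8, t = 2.3646:
- CVb 27.1%: σb = 0.2662, exp(0.2226) − 1 = 25%
- CVb 36.1%: σb = 0.3500, exp(0.2926) − 1 = 34%

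Two such intervals of equal width separate only when the dose-normalised ratio is below exp(−2 × 0.2226) = 0.64, or exp(−2 × 0.2926) = 0.56.

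**3. What the paired contrast would give.** Upper half-width of the 90% CI = exp(t(0.95, n−1)·σw·√(2/n)) − 1, for one day, complete pairs:

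| n | CVw 17.6% | CVw 23.2% | CVw 30.9% | CVw 36.7% |
|---|---|---|---|---|
| 10 | 15.4% | 20.6% | 28% | 34% |
| 8 | 18.0% | 24.2% | 33% | 40% |
| 6 | 22.5% | 30.5% | 42% | 51% |

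At n = 8 and the Part B CVw, the interval excludes 1 for an observed ratio below 1/1.180 = 0.85 or 1/1.242 = 0.81. At the 95% level the half-widths are 22.9% and 31.1%, so the limits are 1/1.229 = 0.81 and 1/1.311 = 0.76. The difference from step 2 is therefore not just the confidence level. Part of it is that non-overlap is a strict criterion. The part due to pairing is the ratio of standard errors: 0.2662/0.1747 and 0.3500/0.2290, both about 1.5.

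The ordering survives the larger Part A values. At n = 8, CVb of 48.7% and 58.5% give σb = 0.461 and 0.543, and per-dose 95% half-widths of exp(0.386) − 1 = 47% and exp(0.454) − 1 = 57%. The paired 90% half-widths are 33% and 40%.

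**4. Dose normalisation.** The modelled endpoints are not dose-normalised. Subtracting ln(240/120) = ln 2 from the log-scale contrast and both its limits gives the dose-normalised ratio. The width does not change.

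**5. What can be separated.** The dose-by-day design for 120 fasted, 240 fasted and 300 fed has rank 6. Adding a fed-state column leaves it at 6; so does adding period columns. So 300 mg cannot be separated from the meal, and no dose contrast can be separated from period (120 mg in Period 1, 240 mg in Period 2, 300 mg in Period 3).

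**The case against.** The SAP follows the protocol. Protocol 10.4.1 plans descriptive summaries and dose-normalised plots for this objective, 10.1 tests no formal hypothesis, and 10.2.2 plans precision for means, not ratios. That stands, and it is why this is an improvement and not a departure. It is a weaker defence of the omission itself, because 10.4.1 promises only description for Part C's dose objective too, and the SAP still added FrelDOSE there.

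A reader might infer that the dose objective gets no estimate or interval at all. The documents do not support that: Table 3.11 and Figure 3.12 supply dose-normalised geometric means with 95% CIs. Only the between-dose ratio is missing.

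A reader might also assume that every evaluable participant contributes both fasted doses. Protocol 5.2 requires only two or more dose levels, and replacements begin at the withdrawn participant's next planned treatment. Six evaluable participants need not mean six 120/240 pairs. Nor is 240 vs 120 mg free of confounding, since it is aliased with period in this fixed sequence. The planned Part A and Part C contrasts share that limit.

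The Day 3 vs Day 1 ratios are not idle either: the endpoints are defined on both days, and reporting the ratio at each dose shows whether repeat-dose behaviour differs by dose. Finally, Parts A and B were complete before Part C was added (protocol 3.1), so the contrast would be specified late and can affect only how Part B is reported.

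**Conclusion.** The point holds as a free improvement of low severity. For its dose objective, Part B has per-dose estimates with intervals but no between-dose ratio with a CI, while the model to produce one is already planned. A paired 240 mg vs 120 mg ratio would have a 90% CI upper half-width of about 15% to 21% (n = 10), 18% to 24% (n = 8) or 23% to 31% (n = 6) at the protocol's Part B CVw, and 28% to 34%, 33% to 40% or 42% to 51% at the Part A-based CVw.

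These widths assume complete pairs and n−1 degrees of freedom; with 2n−2, the n = 8 Part B figures fall to 16.6% and 22.3%. The Part B CVw values are planning values from an IR capsule at 20 mg, set at about 0.65 of CVb (17.6/27.1, 23.2/36.1), so the gain from pairing is assumed, not observed. The Part A values are single-dose but come from this study. At the wider end, the ratio would detect only large departures from proportionality, and it covers one two-fold step.

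**What to change.** In SAP 8.2.5.2 (results presentation), the comparison list in 10.6.4 and Table 3.12, add from the same mixed model the log-scale 240 mg minus 120 mg contrast, both fasted, less ln 2, on Day 1 and on Day 3. Back-transform it to a dose-normalised geometric mean ratio with a 90% CI. Report the number of participants with both doses. Keep Table 3.11, Figure 3.12 and the Day 3 vs Day 1 ratios.

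Add a footnote that the contrast compares Period 2 with Period 1 and cannot be separated from a period effect, and that any contrast with 300 mg also mixes dose with the standard meal. Mark it as added after Part B was complete.

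The cost is two contrasts per endpoint in a model already planned, one footnote and a few table rows. It needs no new data, procedures or participants.
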